6.2 Study end-points

Does repeated administration of CVS improve symptoms in Parkinson's Disease?

9.1 Analysis of Risk/ Benefit

We have previously conducted three NRES REC approved studies that have applied CVS (via the device described above) to neurological patients. Two of these studies have focused on patients with severe traumatic brain injury (in one study these patients were too disabled to self-consent): (i) Rec Ref: 14/EE/1041; An Initial Investigation into the Utility of Caloric Vestibular

Stimulation as a Treatment in Traumatic Brain Injury, and (ii) Rec Ref: 12/LO/0492 Does Vestibular Stimulation Aid Recovery From Low Awareness State? The third study (Rec Ref: 12/LO/1354 A non-invasive neuro-modulation device for migraine headache) focused on episodic migraine. All three studies utilized a similar treatment and assessment protocol to that proposed here and have not reported any serious events or reactions that could be associated with the study.

As noted previously, the aims of this Study involve the mitigation of neuropsychiatric symptoms in the PD subject population. Given the limited options available to the subjects who will be enrolled in the Study, improvement in their overall symptom burden will be viewed as significant. The CVS device is subject to the risks outlined below.

(1) Biocompatibility/toxicity

Biocompatibility is believed to be a minimal risk based on the selection and use of well-characterized materials. In addition, biocompatibility of the aluminum earpieces will be assessed in accordance with the requirements of ISO 10993.

(2) Infection control

Users are instructed to clean the device frequently (the earpieces and the surfaces touching the skin). The users are instructed to use 70% isopropyl alcohol wipes. This cleaning procedure will be independently validated.

(3) Side-effects

Adverse events associated with the application of CVS:

- The risk associated with the use of the CVS device is anticipated to be minimal (classified by the FDA for use in migraine as 'non-significant'). Mild nausea, dizziness and drowsiness are hallmarks of activation of the vestibular system, represent anticipated responses to this therapy and thus are not regarded as unanticipated side effects or AEs. The intensity of these symptoms is dose-dependent and reversible with discontinuation of the thermal stimulus. These symptoms typically resolve within 5-10 minutes after the discontinuation of stimulation.
- The primary, low-probability risks associated with use of the device include ear canal irritation and activation of Arnold's nerve with associated cough reflex. Ear canal irritation, if present, should resolve within several hours after the therapy has been discontinued.
- To date, studies conducted by the chief investigator have experienced no unanticipated or serious side effects with the use of the CVS device.
- The device is not an implantable device or for use in supporting or sustaining human life. While it is planned for treatment of PD symptoms, it is transcutaneous and not expected to represent a potential for serious risk to the health, safety, or welfare of a subject. The risks of use of the CVS device are similar to or the same as those experienced when using CVS for vestibular function testing of a patient's body balance system.

- In a review of the guidance document, "Information Sheet Guidance for IRBs, Clinical Investigators, and Sponsors, Significant Risk and Non-significant Risk Medical Device Studies: January 2006", the list of non-significant risk devices includes devices with similar characteristics and functions to the device that we will use, such as: (1) Functional non-invasive electrical neuromuscular stimulators, (2) Low power lasers for treatment of pain, and (3) Transcutaneous electric nerve stimulation (TENS) devices for treatment of pain other than angina/chest pain.

(4) Software malfunction

The software for the device has been validated by an independent software engineering firm in accordance with FDA's guidance, "Guidance for the Content of Premarket Submissions for Software Contained in Medical Devices: May 11, 2005". This guidance has been used for establishing the software level of concern and the developmental documentation requirements, as well as for determining the appropriate verification and validation testing.

(5) Home Use

The PD study plans to permit both "in-clinic" and "at-home" use of the device following an initial training session conducted with the patient and their carer under the supervision of the study team. If after the training session the Study coordinator concludes that the subject is ready, the subject will then be allowed to continue twice-daily treatments at home until the end of the treatment period. The patient will be instructed that if she or he has any questions or encounters any issues at home, the patient should immediately call the Study coordinator. If the Study coordinator concludes that the patient is not ready for self-treating at home and that additional training is needed, the patient will be instructed to return to the clinic the next day (when possible) to receive such additional training.

The device contains software features that allow physician control of the patient-specific treatment: controlling application time, temperature, waveform, and number of treatments. Safety lockouts prevent over-use by patients by limiting the prescription and the number of applications per day. Throughout the study, patients are required to complete interim assessments for continued evaluations and monitoring.

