3.2 Stopping criteria

We plan to administer multiple exposures to CVS in order to encourage experience-dependent long-term plastic change (Hoffman et al., 2002). We will study patients for a maximum of 16 weeks allowing for up to 8 weeks of stimulation. Our previous studies suggest that a 16 week protocol is likely to be feasible for patients and carers to commit to without becoming overly burdensome.

The trial will be stopped if the study clinicians (Drs [name]/[name]) and the chief investigator ([name]), or the local NHS R&D unit or sponsor, agree that a critical number of AEs have been reported. The trial may also be terminated if participants and their carers fail to comply with the stimulation protocol (2 x stimulation sessions per each day).

4. Study Design

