6.1 Plan and Statistical Considerations

Comparisons of scores on the behavioural measures in active and inactive (active, placebo) patients will be completed using formal parametric / nonparametric repeated measures tests. The results will be presented as group means (idiopathic cohort 1 and 2) with corresponding confidence intervals. Tests for assumptions will be conducted prior to analysis. For the electrophysiological measures, ANOVA will be used to compare elements of the ERP and more global aspects of the EEG across alternating blocks of active and sham stimulation.

If the active group is shown to be statistically superior to the placebo group then those in the placebo group will be offered the active treatment at the end of study. If there is evidence, as determined by the independent statistician, that a more prolonged treatment schedule may confer greater benefit then the placebo group will be offered the opportunity to receive 4 months of active treatment instead of the current 2. Regardless of whether 2 or 4 months of treatment is received, participants will repeat the assessment schedule that they completed during their earlier treatment phase, with the exception of EEG which given its time-consuming and burdensome nature will be dropped.

Adverse events, general concerns, dropouts and satisfaction will be presented as summary statistics for each group.

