9.2 Monitoring of Research

The safety of this study will be regularly reviewed by the research team who will examine the specific study protocol, assess its risks and benefits, interpret the data, and assure that the study is conducted in the safest and most effective manner.

Although the proposed procedure is associated with minimal risk to subjects, the research team will regularly convene to monitor safety by reviewing AE reports and making future recommendations regarding appropriate safety procedures and proper use and interpretation of data to assure that subject participation is worthwhile.

9.2A Adverse Events

An AE includes any noxious, pathological or unintended change in neurological or bodily function as indicated by physical signs that occurs during the trial, regardless of whether it appears related or unrelated to the treatment.

All AEs will be graded for severity using the following criteria: Grade 0 = (none); Grade 1 = mild: No effect on activities of daily living; Grade 2 = moderate: partial limitation in activities of daily living; Grade 3 = severe: considerable limitation in activities of daily living—medical evaluation required. All AEs will be recorded by the patient and their carer/ care team on an individual diary card or directly to a member of the research team who will record the event using an AE form. A serious adverse event (SAE) is an AE that meets one of the following conditions: death, life-threatening situation (i.e. seizure), hospitalization, severe disruption of daily activity. If an SAE occurs during testing then immediate medical attention will be given from medical personnel at the on-site hospital facilities or by a qualified first-aider. Assessment and monitoring of AEs that occur between sessions will be based on verbal report by the patients and their carers. Patients and their carers will be given contact details so that they are able to report an AE to the research team at any time.

All AEs will be recorded using AE forms which will bear the subjects ID number and will remain on their secure electronic file visible to all members of the research team.

9.2B Discontinued Subjects

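### Protocol 9.1 can be read as exempting mild nausea, dizziness and drowsiness from the adverse event (AE) definition in 9.2A, which would understate any tolerability difference between the arms

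*Protocol*

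**What the plan says.** Protocol 9.1, under (3) Side-effects, opens a list titled "Adverse events associated with the application of CVS". Its first bullet says "Mild nausea, dizziness and drowsiness are hallmarks of activation of the vestibular system", and that these symptoms are expected responses to the treatment and "thus are not regarded as unanticipated side effects or AEs". It adds that their intensity depends on dose and that they usually pass within 5 to 10 minutes of the end of stimulation.

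Protocol 9.2A gives the definition for recording: "An AE includes any noxious, pathological or unintended change in neurological or bodily function". The same sentence goes on to require that the change show itself in physical signs, and it includes events whether or not they seem related to treatment. All AEs are to be graded and recorded, and the scale has a mild level: "Grade 1 = mild: No effect on activities of daily living". No exception is made for expected effects, and neither section refers to the other.

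The AE record has three uses. Section 6.1 says "Adverse events, general concerns, dropouts and satisfaction will be presented as summary statistics for each group". Section 9.2C promises tables of AE frequency for the research team's review. Section 3.2 allows the trial to be stopped if the responsible parties "agree that a critical number of AEs have been reported".

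The SAP contains no AE definition and no AE analysis.

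**The concern.** Two people following this protocol could classify the same mild dizzy spell differently: one as a Grade 1 AE under 9.2A, the other as no AE under 9.1. The difference would not be neutral between the arms. The protocol attributes these symptoms to vestibular activation, and section 3.1 says that the unpowered placebo device gives no material vestibular stimulation. An exemption worded without reference to arm would therefore remove events mainly from the active arm. The by-group AE summary would then understate any difference in tolerability, in a pilot whose results are meant to inform a larger trial.

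**Working it through.** No figure in the documents bears directly on this point, so there is none to reproduce. The check is a comparison of the text, followed by an illustration of size.

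**Step 1: classify one mild, brief dizzy spell during an active session.**

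| Reading | Basis | Counted as an AE? |
|---|---|---|
| A. 9.1 exempts it | Expected responses are not AEs | No |
| B. In 9.1, 'unanticipated' governs both nouns, so 9.1 says only that it is not an unanticipated AE | 9.2A then applies | Yes, Grade 1 |
| C. 9.2A alone, with its physical-signs condition read strictly | A purely subjective symptom may not qualify | Perhaps not |

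The wording allows all three. Reading B is possible, but 9.2A does not divide AEs into anticipated and unanticipated. One might say that an expected effect is not unintended, but 9.2A also covers noxious changes, and nausea fits that word. Reading C means that a bare statement that 9.2A governs would not ensure that these symptoms are recorded.

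**Step 2: which arm loses events.** Nothing in 9.1 limits the exemption to one arm. The imbalance follows from 3.1 (earpieces unpowered, no temperature gradient) together with 9.1 (symptoms caused by vestibular activation). Mild symptoms from other causes could occur in either arm.

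**Step 3: exposure.** Protocol 4.2 and the SAP design table give 16 active participants, 2 sessions a day, 7 days a week for 8 weeks:

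16 × 2 × 7 × 8 = 1,792 active sessions.

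This assumes full compliance and no dropout.

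**Step 4: illustration with assumed rates.** The documents give no rate, so these values only show a range.

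- By session: 1% gives 1,792 × 0.01 ≈ 18 events, 5% gives about 90, and 20% gives about 358.
- By participant, with no mild events on placebo:

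| Assumed share of active participants with at least one mild event | Affected, of 16 | Difference if counted | Difference under reading A |
|---|---|---|---|
| 10% | 1.6, about 2 | 2/16 = 12.5 points | 0 |
| 30% | 4.8, about 5 | 5/16 = 31 points | 0 |
| 50% | 8 | 8/16 = 50 points | 0 |
| 70% | 11.2, about 11 | 11/16 = 69 points | 0 |

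If one placebo participant also had a mild event, the second row would become 5/16 − 1/16 = 4/16 = 25 points. The last column refers to the mild exempted symptoms only. The plan describes no test of AE rates, so I give counts and differences and no p-values.

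**The case against.** The strongest reply is that 9.1 is a risk-benefit description and that 9.2A holds the recording rules. On that view 9.1 only calls the symptoms expected, and its list title already calls them adverse events. This is a fair reading, and it is why the point is that 9.1 *can* be read as an exemption. The phrase still reaches AEs in so many words, and nothing tells staff to set it aside.

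Several stronger conclusions are tempting, and the documents do not support them.

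- A reader might infer that the commonest device effects will vanish from the report. The protocol calls these symptoms hallmarks, and calls ear irritation and cough low-probability risks, but it gives no frequencies. The exemption covers mild symptoms only. Section 6.1 also summarises general concerns and satisfaction, and Annex 1 includes diary entries and a closing interview about the device. These are not AE counts, but they mean that the symptoms need not go wholly unseen.
- A reader might infer that tolerability is a main output of the pilot. The stated purposes are effect sizes (Protocol 5.2) and variances (SAP section 4), and the SAP lists no safety outcome. The AE summary is descriptive.
- A reader might infer that the stopping safeguard is weakened. Section 3.2 gives no number and relies on agreement among named parties, so whether brief mild symptoms would affect that decision cannot be told.

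**Conclusion.** The point holds as an unresolved conflict that should be fixed. Sections 9.1 and 9.2A can classify the same mild event differently, and nothing in the protocol or SAP decides between them. If 9.1 is applied as an exemption, the by-group AE summary and the frequency tables would understate any tolerability difference, because the missing events would come mainly from the active arm.

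The direction rests on the protocol's own account of the sham and of what causes the symptoms. The size is unknown and depends on a symptom rate that the documents do not give; the event counts also assume full compliance. Moderate and severe events, serious adverse events, randomisation and the efficacy analyses are not affected. The effect on the stopping review is uncertain. It would go too far to conclude that a given number of events will be lost: the text shows that they can be left out, not that they will be.

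**What to change.** 1. In 9.1, delete the words 'or AEs', so that the sentence says only that these symptoms are not unanticipated side effects.
2. In 9.2A, state that patient-reported nausea, dizziness and drowsiness are recorded in both arms whether or not there are physical signs. Grade them 1 to 3 (Grade 0 means none, so a recorded event cannot carry it) and flag them 'anticipated, device-related'. Assign the flag by symptom, in the same way in both arms.
3. In the 6.1 summary and the 9.2C tables, show these events by arm on a line separate from other AEs, as participants with at least one event and number of events. The safety review then sees anticipated and other events separately, and frequent mild symptoms do not swamp the rest.
4. State in the AE report which definition was used.

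The cost is protocol wording, more diary entries, and a less favourable reported AE rate in the active arm. Treatment, visits and sample size do not change. The flag keeps the sponsor's legitimate point that these effects are expected and reversible.

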9.2 Monitoring of Research

The safety of this study will be regularly reviewed by the research team who will examine the specific study protocol, assess its risks and benefits, interpret the data, and assure that the study is conducted in the safest and most effective manner.

Although the proposed procedure is associated with minimal risk to subjects, the research team will regularly convene to monitor safety by reviewing AE reports and making future recommendations regarding appropriate safety procedures and proper use and interpretation of data to assure that subject participation is worthwhile.

9.2A Adverse Events

An AE includes any noxious, pathological or unintended change in neurological or bodily function as indicated by physical signs that occurs during the trial, regardless of whether it appears related or unrelated to the treatment.

All AEs will be graded for severity using the following criteria: Grade 0 = (none); Grade 1 = mild: No effect on activities of daily living; Grade 2 = moderate: partial limitation in activities of daily living; Grade 3 = severe: considerable limitation in activities of daily living—medical evaluation required. All AEs will be recorded by the patient and their carer/ care team on an individual diary card or directly to a member of the research team who will record the event using an AE form. A serious adverse event (SAE) is an AE that meets one of the following conditions: death, life-threatening situation (i.e. seizure), hospitalization, severe disruption of daily activity. If an SAE occurs during testing then immediate medical attention will be given from medical personnel at the on-site hospital facilities or by a qualified first-aider. Assessment and monitoring of AEs that occur between sessions will be based on verbal report by the patients and their carers. Patients and their carers will be given contact details so that they are able to report an AE to the research team at any time.

All AEs will be recorded using AE forms which will bear the subjects ID number and will remain on their secure electronic file visible to all members of the research team.

9.2B Discontinued Subjects

Subjects may be discontinued if they fail to meet the requirements of the protocol or meet one of the withdrawal criteria specified above. Patients are expected to complete two daily sessions of stimulation (an hour apart) and attend regular assessments. If participants fail to meet these expectations the chief investigator will review the patient's records and decide whether termination of their participation is required.

Discontinued subjects will be replaced until the study has met its participant quotient.

9.2C Process of Review

The research team will meet in person if required. We will provide summary tables categorizing and reporting the frequency of AEs. We will also compile and present data on the number, gender and ethnicity of subjects. We will summarize on the number of dropouts from the study, and the reason for withdrawal.

9.2D Committee Report and Compliance with Recommendations

After each meeting, the chairperson of the research team will prepare a summary of their meeting with appropriate recommendations. The report will be distributed amongst the team and the R&D departments of the participating trusts.

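### The adverse event definition is tied to physical signs and silent on symptoms and mental state, so it can be read as leaving out the harms that diary cards and verbal reports would mostly bring in

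*Protocol*

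**What the plan says.** Protocol 9.2A opens its definition with "An AE includes any noxious, pathological or unintended change". The class of change it goes on to describe is "any noxious, pathological or unintended change in neurological or bodily function as indicated by physical signs that occurs during the trial", and it applies whether or not the event is related to treatment. Symptoms and mental state are not mentioned there, and no other section of either document adds them.

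On collection, the same section says "All AEs will be recorded by the patient and their carer/ care team on an individual diary card or directly to a member of the" team running the study. It then adds: "Assessment and monitoring of AEs that occur between sessions will be based on verbal report by the patients and their carers". Severity is graded by how far daily activities are limited.

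Serious events are a subset: "A serious adverse event (SAE) is an AE that meets one of the following conditions". Section 9.1 says of mild nausea, dizziness and drowsiness that they "represent anticipated responses to this therapy and thus are not regarded as unanticipated side effects or AEs".

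On reporting, 6.1 says "Adverse events, general concerns, dropouts and satisfaction will be presented as summary statistics for each group", and 9.2C says "We will provide summary tables categorizing and reporting the frequency of AEs". Section 3.2 allows the trial to stop if the named parties agree that AEs have reached a critical number, which it does not specify. The SAP lists no safety outcome and no AE analysis.

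**The concern.** A sign is something an observer can find; a symptom is something the participant reports. The definition speaks of the first, while the collection method mostly yields the second. A participant at home who reports a new complaint with nothing visible on examination gives the team a report that the definition does not clearly cover.

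This matters more here than in many device trials. Section 9.1 places relief of neuropsychiatric symptoms among the aims, and 2.1 lists anxiety, depression and cognitive dysfunction as part of the disease. A treatment intended to improve mental state could also worsen it, yet the definition does not name that as a harm.

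Blinding adds a further risk. Section 4.3 and SAP section 2 describe a single-blind trial in which participants do not know their allocation, and no blinding of staff is described. If staff who know the arm decide whether a sign-free complaint counts, an unclear definition could distort the comparison between arms as well as lower the total.

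**Working it through.** No formula applies, and the plan states no figure that depends on the definition. The check compares two readings of 9.2A with the other provisions.

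**Reading A (narrow):** an AE needs physical signs. **Reading B (wide):** the sentence gives one class of AE, and symptoms may also count.

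1. *The qualifier in 9.2A.* It favours A. Under B, the reference to physical signs does little work.
2. *The opening verb in 9.2A.* It favours B, because includes does not close the list.
3. *Diary card, direct report and verbal report (9.2A).* These favour B. Under A, the main sources would produce much material that could not be counted.
4. *Severity grading by limitation of daily activities (9.2A).* This favours B, since grading needs no examination finding.
5. *The exclusion of mild nausea, dizziness and drowsiness (9.1).* This favours B. They are removed because they are anticipated, not because they lack signs. Under A, such largely subjective complaints would hardly need removing.

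The text therefore supports both readings, and most of the surrounding provisions lean towards B. To see the consequence, take one report: a participant says between sessions that mood has become markedly worse, with no physical sign. (The example is mine; neither document names it as an expected or excluded harm.)

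- Under A it is not an AE. It cannot then be a serious event, because those are defined within AEs. It enters neither the 6.1 nor the 9.2C AE summary, and it does not count under 3.2.
- Under B it is an AE and enters all of these.

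Taken literally, A would also leave out a hospital admission for psychiatric deterioration without physical signs. Ear canal irritation, which 9.1 lists among the primary device risks, is a further case if it is felt but not visible.

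Scheduled exposure is 2 sessions × 7 days × 8 weeks = 112 sessions per participant (4.2; SAP section 2). Section 9.1 permits use both in clinic and at home. The figure shows that many sessions may take place with no examiner present. It does not measure how many events would be misclassified.

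**The case against.** The strongest reply is that a team following 9.2A as a whole would simply record a reported headache. The section is built around patient and carer report, its list is not closed, and 9.1 treats symptoms as things that would be AEs unless exempted. Nothing in the documents says that reports are screened for signs or discarded. This stands, and it defeats the stronger inference a reader might draw, that the definition requires signs and so shuts out symptom-only and psychiatric harms. The documents do not establish that.

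A second reply is that such complaints have other routes. Section 6.1 summarises general concerns by group. Section 9.1 tells patients to call about any issue at home, and Annex 1 provides for diary entries, contact during treatment and a closing interview. HADS, the NMSS and MDS-UPDRS 1 are analysed by arm (SAP section 3). This stands in part. General concerns are undefined and ungraded, and they lie outside the serious-event and stopping provisions. The scales give scheduled scores, and a mean change is not a count of events.

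A third reply is that the unspecified critical number in 3.2 is a larger weakness than the wording of the definition. That may be so, but any such number still depends on what is counted.

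**Conclusion.** The definition is ambiguous. Its narrow reading would leave harms without physical signs out of the AE and serious-event counts, and that reading conflicts with the section's own means of collection. The wide reading avoids the exclusion but does not tell a participant, carer or form user which symptoms count, so inconsistent classification remains possible under either.

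The size of the effect cannot be derived. The documents give no rate for symptom-only events and do not say how reports are classified. It would also go too far to say that a safety outcome is biased, because no safety outcome is formally defined: the protocol plans descriptive AE summaries and the SAP plans none.

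The conclusion assumes that the AE form and diary card, which are not reproduced in the documents, do not already settle the matter. The point affects how far the trial's safety description can be relied on; it does not touch the efficacy analysis. It is worth correcting because one sentence is enough.

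**What to change.** In Protocol 9.2A, replace the words that tie an AE to neurological or bodily function shown by physical signs with: *in physical, neurological or mental state, shown by signs or reported as symptoms by the participant or carer*. The serious-event definition then follows without further change.

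Reconcile 9.1 with 9.2A, so that an event set aside because it is anticipated is clearly distinguished from one set aside because it lacks signs. Align the AE form, and include symptom-only events in the by-group AE summary under 6.1.

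If data collection is complete, the existing diary cards and AE forms can be reviewed again under the clarified wording, and the report should state which definition was applied during the trial. The wording could still matter for future exposure, since 6.1 provides for offering active treatment to the placebo group if the active group proves superior.

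The cost is one sentence, matching form text, more minor events to record and a higher reported AE count.
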